#### Sample Recruitment:

Patients and caregivers will be recruited from WCM. Experts will be recruited through relevant professional societies (e.g., American Psychosocial Oncology Society) and the professional networks

(e.g., Cancer Support Community) of study team members. For Aim 1, n=10 patient-caregiver dyads and n=10 psychosocial oncology experts will be recruited. For Aims 2 and 3, n=30 advanced cancer patient-caregiver dyads will be enrolled, consistent with the recommendations of the Stage Model of Behavioral Therapies Research for evaluation of feasibility and clinically significant change. Sampling and recruitment procedures outlined here have been used for similar studies (e.g., CwC I, II, and III) with recruitment rates of 70%. The proposed recruitment procedures for experts have been successfully used in a similar intervention development study (K23 AG048632, PI: [name]).

#### Proposed analyses:

**Aim 1.** Data coding and analysis will be informed by a responsive interviewing model in which data units, or "blocks of information" are combined based on the theme they represent. Trained raters will independently review the transcripts and identify passages that include suggestions for modifications to the intervention. Raters will then organize these passages into categories reflecting single themes. Research team members will discuss these themes and make revisions until consensus is reached on the themes of the interviews. The themes identified in this analysis will inform modifications to the intervention.

**Aim 2.** Feasibility and acceptability will be examined by conducting frequency and descriptive statistics (i.e., mean, median, standard deviation) for enrollment rates, number of sessions completed, number of weeks required to complete the intervention, and Likert-scale items assessing satisfaction with the intervention and perceived helpfulness. We will conduct qualitative analyses on the open-ended questions as in Aim 1. Benchmarks: The benchmark for feasibility is  $\geq 60\%$  of screened eligible dyads enroll in the study. Further,  $\geq 70\%$  of dyads who enroll in the study will complete 75% of the intervention sessions. For acceptability,  $\geq 70\%$  of dyads will have an average score of greater than or equal to 2 on Likert scale items assessing perceived acceptability of 'moderately' (2) to 'very' (4) acceptable on a 0-4 scale.

**Aim 3.** Aim 3 will be addressed using a pre-post design. To account for the non-independence of the dyadic nature of the data (i.e., patients' and caregivers' ratings are expected to be correlated), we will use generalized linear mixed modeling (GLMM) for continuous and binary/dichotomous outcomes. A post-versus-pre- difference will be sought to estimate the rate of increase of dyads pre/post to determine the degree to which the communication-based intervention is likely to improve patient and caregiver outcomes in: patients' and caregivers' accurate prognostic understanding, engagement in ACP, completion of ADs, receipt of goal-concordant care, healthcare utilization rates, psychological distress, communication quality, and caregiver burden. Missing data. To reduce missing data, study staff will conduct interviews rather than relying on written self-reports. After attempts are made to reduce the amount of missing data, all remaining data will be assessed for missingness (e.g., random or non-random). Based on these results, the appropriate imputation methods will be used to handle missing data. Due to the ill nature of this population, it is estimated that some data will be missing not at random due to mortality of patients. As such, proper methods will be taken to deal with this data. Because this is a pilot study, sample sizes were determined based on prior recommendations for pilot pre-/post- intervention designs. Although this study will not be sufficiently powered to detect efficacy, it will allow for testing of feasibility, acceptability, and preliminary efficacy.

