## STUDY DESIGN

### Aims, research questions, and hypotheses:

The objective of the proposed study is to develop and pilot test an intervention that improves patient and caregiver prognostic understanding (terminal nature of illness, life-expectancy) using theoretically grounded techniques of distress tolerance (inhibitory learning theory) and communication skills (cognitive-social processing theory). This objective will be met using a mixed-methods approach across three specific aims: Aim 1: To develop an intervention to improve advanced cancer patients' and caregivers' prognostic understanding using communication (validation of fear) and distress management (deep breathing) techniques. Aim 2: To evaluate the feasibility and acceptability of the patient-caregiver communication-based intervention among advanced cancer patients and their caregivers. Hypothesis 2a: To evaluate feasibility, greater than or equal to 70% of participants will meet the benchmark for feasibility defined by participant retention and adherence to the intervention. Hypothesis 2b: To evaluate acceptability, greater than or equal to 70% of participants will meet the benchmark for acceptability defined by responses on self-report measures of perceived helpfulness, satisfaction, and impact. Aim 3: To test the preliminary efficacy of the intervention on patients' and caregivers' prognostic understanding (primary outcome); completion of a DNR order, living will, and health care proxy; psychological distress; communication outcomes). Hypothesis 3: We hypothesize that the intervention will improve patients' and caregivers' prognostic understanding and communication quality; increase completion of DNR/proxy/living wills and receipt of goal-concordant care; and reduce distress, caregiver burden, and receipt of aggressive futile care. The current intervention consists of seven 45-minute telephone-delivered sessions. For Aim 1, we will collect feedback from advanced cancer patients and their caregivers ( $n=10$  dyads) and psychosocial experts ( $n=10$ ) to improve and refine the intervention. For Aims 2 and 3, we will pilot test the intervention with  $n=30$  patient-caregiver dyads and assess outcomes at baseline, post-intervention, and three months later. Study Design Overview: To achieve Aim 1, we will let our developed preliminary intervention materials with advanced cancer

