#### INCLUSION AND EXCLUSION CRITERIA

Patient eligibility requirements: (1) diagnosis of poor prognosis advanced cancer defined as locally advanced or metastatic cancer (e.g., pancreaticobiliary, esophagogastric, hepatocellular carcinoma,

lung, or gynecological cancer) and/or disease progression following at least first line chemotherapy; (2) ability to provide informed consent; (3) identification of an informal caregiver; and (4) oncologist reported discussion of prognosis with the patient and/or caregiver. These criteria have been successfully used in prior research by our study team to identify patients with a prognosis of 6 months or less to live. Caregiver eligibility requirements: (1) the person the patient indicates provides their informal (unpaid) care; (2) English speaking; and (3) able to provide informed consent. Expert eligibility requirements (Aim1 only): (1) current clinical practice and/or research with advanced cancer patients and; (2) a history of 5+ years working with advanced cancer patients. Experts across disciplines (e.g., social work, psychology) will be enrolled.

Patient exclusion criteria: (1) not fluent in English; (2) severely cognitively impaired (Short Portable Mental Status Questionnaire scores of < 6); (3) too ill or weak to complete the interviews (as judged by the interviewer); (4) receiving hospice at the time of enrollment; (5) younger than age 18; (6) deemed psychologically inappropriate for the study by their treating oncologist. To help guide referring physicians, a guide has been compiled to help define who could be considered psychologically inappropriate. This could include: a patient being too distressed by their current diagnosis, prognosis, or treatment regimen and likely to have that distress exacerbated by being approached for this study. Additional exclusion criteria include: (7) reports alcohol abuse or dependence; (8) reports abuse or dependence of another drug (like cocaine or heroin); (9) meets diagnostic criteria for a severe psychiatric disorder, including bipolar disorder, schizophrenia, or other psychotic disorders; and (10) states that they currently endorse suicidality, including a plan and intent to attempt a suicide. Patient-caregiver dyads in which both members have an accurate understanding of prognosis (terminal status and life-expectancy) will be excluded due to the lack of need for an intervention.

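### Does excluding dyads who already understand the prognosis build a false gain into the uncontrolled pre/post estimate of the primary Aim 3 outcome?

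*Combined protocol and SAP*

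**What the plan says.** The exclusion rule, in the section on inclusion and exclusion criteria, reads: "Patient-caregiver dyads in which both members have an accurate understanding of prognosis (terminal status and life-expectancy) will be excluded". The stated reason is that such dyads do not need the intervention.

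The section on aims, research questions and hypotheses builds the outcome from the same two components. The objective is an intervention that "improves patient and caregiver prognostic understanding (terminal nature of illness, life-expectancy"), and Aim 3 is "To test the preliminary efficacy of the intervention on patients' and caregivers' prognostic understanding (primary outcome"). The same section says the team will "assess outcomes at baseline, post-intervention, and three months later".

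Under Proposed analyses, Aim 3 is a single-group pre-post comparison: "A post-versus-pre- difference will be sought to estimate the rate of increase of dyads pre/post", used "to determine the degree to which the communication-based intervention is likely to improve patient and caregiver outcomes". A generalized linear mixed model (GLMM) is chosen because "patients' and caregivers' ratings are expected to be correlated". The same paragraph says the study lacks the power to detect efficacy.

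The Aim 2 paragraph counts the share "of screened eligible dyads enroll in the study", so eligibility is settled before enrolment. Nowhere do the documents say whether the screening answers or a new baseline reading supply the pre value.

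**The concern.** A dyad enters only if at least one member gave an inaccurate answer at screening. Some of those answers will be momentary: a person who usually understands the prognosis may answer inaccurately on one day. Asked again, a few such dyads will look both-accurate with no help from the intervention. Dyads that erred in the other direction were excluded, so nothing offsets this. With no control arm, the drift adds to the estimated gain and is favourable in expectation.

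There is also a modelling worry. If the outcome is a both-accurate indicator per dyad and the screening answers are the pre value, the baseline is 0/30 by construction. A logistic GLMM then has no finite time effect once any dyad converts. At stake is whether the preliminary efficacy estimate for the primary Aim 3 outcome could be partly or wholly an artefact.

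**Working it through.** **Inputs.**
- Dyads: n = 30 (Sample Recruitment). The plan bases this on pilot-study recommendations and gives no alpha, power or effect size, so there is no calculation to reproduce.
- Both-accurate rate before exclusion: q = 9.6% of 178 dyads (Background). Check: 17/178 = 9.55%. This figure covers life expectancy only. Requiring terminal status as well could only lower it in that cohort. The eligibility condition that the oncologist reports a prognosis discussion could raise it.
- Retest agreement: not in the documents. Kappa k = 0.8 to 0.5 is assumed.
- Throughout, no intervention effect and a stable population rate.

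**Case 1: screening answers reused as pre.**

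*Kappa on the dyad indicator.* P(both accurate later | not both at screening) = q(1 − k).
- k = 0.8: 0.096 × 0.2 = 1.9%, and × 30 = 0.6 dyads.
- k = 0.5: 0.096 × 0.5 = 4.8%, and × 30 = 1.4 dyads.

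*Kappa on each member*, with independent members of equal accuracy p = √0.096 = 0.310. An accurate member stays accurate with probability a = p + k(1 − p), and an inaccurate one becomes accurate with probability b = p(1 − k). Among retained dyads, the share with one accurate member is 2p(1 − p)/(1 − q) = 0.473, and with none (1 − p)²/(1 − q) = 0.527. The false rise is 0.473ab + 0.527b².
- k = 0.8: a = 0.862, b = 0.062, giving 2.7%, or 0.8 of 30.
- k = 0.5: a = 0.655, b = 0.155, giving 6.1%, or 1.8 of 30.

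*Member-level outcome.* Exclusion lowers member accuracy p by q(1 − p)/(1 − q), and a fraction (1 − k) of that returns. At p = 30%: 0.096 × 0.70/0.904 = 7.4 points, so the drift is 1.5 points (k = 0.8) to 3.7 points (k = 0.5).

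*Uncertainty in q.* The exact 95% interval for 17/178 is 5.7% to 14.9%. The dyad-indicator rise then runs from 0.057 × 0.2 = 1.1 points to 0.149 × 0.5 = 7.4 points.

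*Cross-check.* A simulation with stable traits plus independent error (latent reliability 0.9 to 0.5, within-dyad correlation 0.2 or 0.4) gave 3.4 to 7.2 points for dyads, 2.2 to 5.2 for patients and 1.7 to 4.2 for caregivers. The direction and order of size agree.

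**Case 2: a separate baseline reading is pre.**

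*Independent answer error.* The regression has already happened by baseline, so the expected both-accurate share is q(1 − k) at baseline and again at post, a difference of 0. The simulation agrees: 5.9% at baseline against 5.8% at post (reliability 0.7, correlation 0.2).

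*Answers that truly shift from visit to visit*, assuming equal gaps: q(1 − k²) − q(1 − k) = qk(1 − k), which is 1.5 points (k = 0.8) to 2.4 points (k = 0.5). Other spacings give other values.

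**Scale.** The exact 95% interval is 0% to 11.6% for 0/30 and 0.1% to 17.2% for 1/30. Every false rise above is below 11.6 points.

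**The case for a change.** The strongest reply is that a small sample and a pilot label excuse random error only. This error is systematic, favourable in expectation, sits in the outcome named as primary for Aim 3, and would not shrink with more dyads. The plan reads the change as informative about the intervention and does not mention regression to the mean. One reading that the text permits also leaves the planned binary model without a finite estimate.

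Part of this stands. The structure is real, the source of the pre value is unstated, and a residual remains even with a separate baseline if answers truly shift.

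The rest is weaker. The plan schedules a baseline outcome assessment, and nothing suggests that screening answers replace it. The 0/30 failure needs two unstated conditions together: screening as pre, and a dyad-level indicator. The second fits poorly with the plan's own reason for the mixed model, because a single indicator per dyad has no patient-caregiver correlation to account for, although the phrase about the increase of dyads leaves some doubt. Members' ratings analysed separately do not start at zero by construction. Any analyst who did meet a zero baseline would see at once that the odds ratio cannot be estimated and would report proportions.

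The exclusion itself is a fair choice. Dyads that already understand the prognosis have no room to improve on the primary outcome, and enrolling them would use up places in a 30-dyad pilot.

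**Conclusion.** The concern describes a genuine mechanism but does not call for a change. On the more natural reading, with a baseline assessment after eligibility is settled, the false gain is about 0 under independent answer error and roughly 1.5 to 2.4 points if answers shift over equally spaced visits. On the less natural reading it is about 2 to 6 points for dyads by formula (up to 7.2 in the simulation), or 1.5 to 3.7 points for members at 30% accuracy. At most that is about 2 of 30 dyads, within the sampling error of the study.

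These sizes rest on an assumed retest kappa of 0.8 to 0.5 and on a 9.6% both-accurate rate from an earlier cohort. A much higher rate among screened dyads would enlarge the first-case figures in proportion.

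Nothing in the plan turns on this number. The only benchmarks are for feasibility and acceptability; Aim 3 has no threshold or go/no-go rule, and the plan already calls its efficacy reading preliminary and underpowered. An uncontrolled pre/post change also mixes in the passage of time, whichever reading is called pre, and that is an accepted limit of the design. Which reading serves as pre, and whether members or dyads are the unit, are details that a competent analyst would settle sensibly from the visit schedule and the model described.

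### Aim 3 reads a single-group pre/post change as the intervention's likely benefit, but the design cannot separate it from change over time or from selection on inaccurate understanding at entry

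*Combined protocol and SAP*

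**What the plan says.** Under Proposed analyses in the combined protocol and SAP, "Aim 3 will be addressed using a pre-post design". The post-versus-pre difference is to be used "to determine the degree to which the communication-based intervention is likely to improve patient and caregiver outcomes", and the listed outcomes run from prognostic understanding to caregiver burden. The mixed model is justified by the correlation between patient and caregiver. No control group, external reference or adjustment for time is described.

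Hypothesis 3, under Aims, research questions, and hypotheses, is worded causally: "We hypothesize that the intervention will improve patients' and caregivers' prognostic understanding and communication quality". It also expects the intervention to "increase completion of DNR/proxy/living wills and receipt of goal-concordant care", and to reduce distress, caregiver burden and aggressive futile care. On size and timing: "we will pilot test the intervention with $n=30$ patient-caregiver dyads and assess outcomes at baseline, post-intervention, and three months later".

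Under Inclusion and exclusion criteria, the patient criteria are said to pick out people expected to live six months or less. An oncologist must already have discussed prognosis with the patient or caregiver. Patients are excluded if "4) receiving hospice at the time of enrollment", which says nothing about later entry. Dyads in which both members already understand the prognosis accurately are also excluded. The Data and safety monitoring plan notes that some participants will be on active cancer treatment.

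The only limit placed on the efficacy reading concerns power: "Although this study will not be sufficiently powered to detect efficacy, it will allow for testing of feasibility, acceptability, and preliminary efficacy".

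**The concern.** A pre/post difference in one group estimates the intervention effect only if the outcome would have stayed level without the intervention. That is hard to assume here. Participants are seriously ill and are followed through the sessions and for three months afterwards. During that time they may receive progression news, a further talk with the oncologist, a palliative care referral or hospice. Any of these could plausibly improve prognostic understanding or prompt a DNR order, proxy or living will. Progression could also push distress and caregiver burden the wrong way and hide a benefit.

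Selection adds to this. Enrolling only dyads not yet both accurate puts that dyad-level outcome at its floor. Any later movement is upward, including movement that merely corrects an unreliable first assessment.

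At stake is what the Aim 3 result may be said to show. As worded, a rise in understanding would be reported as what the intervention is likely to achieve, when the design cannot tell that apart from time and selection. Aim 2, on feasibility and acceptability, is not affected.

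**Working it through.** **No planned figure to reproduce.** The plan says that "sample sizes were determined based on prior recommendations for pilot pre-/post- intervention designs". It gives no alpha, power, effect size or standard deviation for Aim 3, and no rate of change under usual care. What follows illustrates how far background change alone could be mistaken for benefit.

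**Inputs**
- n = 30 dyads in one group (Aims; Sample Recruitment).
- Both-accurate status is 0% at baseline, from the exclusion criteria, taking the eligibility assessment as baseline.
- Intervention effect = 0, by construction.
- q = proportion of dyads that become both accurate from background causes or measurement error alone. The documents do not give q, so it is an assumption shown over a range.
- Test: exact two-sided paired (McNemar) test at 0.05. The plan names a generalized linear mixed model and no threshold, so this test is only a yardstick.

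**Step 1: conversions needed for p<0.05.** With a 0% baseline every discordant pair goes the same way, so p = 2 × 0.5^b for b conversions.
- b = 5: 2 × 0.5^5 = 0.0625
- b = 6: 2 × 0.5^6 = 0.031

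Six conversions are needed.

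**Step 2: chance of six or more with no intervention effect.** P(X ≥ 6), where X is binomial(n, q). For n = 30 and q = 0.20, the expected count is 30 × 0.20 = 6 and P = 0.572. For q = 0.10, the expected count is 3 and P = 0.073.

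| Assumed q | 30 evaluable | 24 evaluable | 20 evaluable |
|---|---|---|---|
| 5% | 0.3% | 0.1% | <0.1% |
| 10% | 7% | 3% | 1% |
| 15% | 29% | 14% | 7% |
| 20% | 57% | 34% | 20% |
| 30% | 92% | 77% | 58% |

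The columns for 24 and 20 dyads are there because the plan expects data to be lost through patient deaths.

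**Step 3: what an interval would and would not show.** With a 0% baseline, the dyad-level change is simply the follow-up proportion. Exact 95% intervals are 2.1% to 26.5% for 3 of 30 (10%) and 7.7% to 38.6% for 6 of 30 (20%). These describe sampling error around the within-group change. They do not include the background part, and a larger sample would narrow them without removing it.

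**Limit of the illustration.** The 0% floor applies to the dyad-level status. One member of an enrolled dyad may be accurate at baseline, so an individual score can fall as well as rise. The lack of a comparator applies to every Aim 3 outcome.

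**The case against.** The strongest reply is that this is a pilot, and that a single arm is a reasonable way to study feasibility. The plan speaks of preliminary efficacy and likely improvement, and it concedes low power. That stands as far as it goes: the plan does not claim full proof, and the single arm need not change. But low power is a matter of precision. No sentence allows that the change may have causes other than the intervention.

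A reader might be tempted to infer more than the documents support:

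- **That background care goes unrecorded.** Healthcare utilization, goal-concordant care and aggressive care are study outcomes and may capture hospice or palliative care. No list of measures is given, so this cannot be settled. What is missing is any stated use of such data as co-interventions, and any visible measure of new oncologist disclosure.
- **That background change always favours Hypothesis 3.** This is plausible for understanding and directives. Distress and burden could move the other way.
- **That an ineffective intervention would be expected to look significant.** Six conversions do give p = 0.031, but six is only the expected count at an assumed 20%. At 10% the chance of reaching six is 7%, and it falls further if dyads are lost. The plan also sets no alpha and no McNemar test. Background change might be modest: an oncologist discussion has already taken place for everyone enrolled, yet these dyads are still not both accurate.
- **That the estimate will size a later trial.** The documents do not say so.

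It is also fair to object that logging background events cannot separate them from the intervention, because the sessions may prompt them. Session 6, for example, plans for future difficult conversations. That stands, and it limits what such a log can be used for.

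**Conclusion.** The point holds as a matter of inference. Aim 3 and Hypothesis 3 attach to the intervention a within-group change that the design cannot attribute to it, and the low-power caveat does not address this. The clearest documented source of bias is the plan's own eligibility rule, which sets both-accurate status at 0% at entry so that it can only stay or rise. Unrestricted later disclosure, palliative care and hospice are a plausible further source for understanding and directives. For distress and burden the direction is uncertain.

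The size is unknown. With zero effect, 30 evaluable dyads and an exact paired test, the chance of a nominally significant rise is about 7% at an assumed 10% background conversion and 57% at 20%. With 20 evaluable dyads the figures are 1% and 20%. These rest on assumed rates and on a test that the plan does not name. They show how strongly the answer depends on a missing quantity and do not estimate the bias.

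**What to change.** 1. **Reword Aim 3 and Hypothesis 3.** State that the analysis estimates within-group change under the intervention plus usual care, reported with confidence intervals, and that this is not an estimate of the intervention effect. State also that the both-accurate rate is 0% at baseline by eligibility, so that any rise includes regression to the mean.

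2. **Optional descriptive record.** At the post-intervention and three-month interviews already planned, record the dates of any new oncologist prognosis discussion. Add palliative care and hospice entry if the utilization measure does not already capture them. Tabulate these beside changes in understanding and directive completion. Do not present the table as a correction for background change, since the intervention may itself prompt some of these events.

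The first change costs only wording. The second adds a few dated items and one table. The downside is a weaker efficacy claim and slightly longer interviews. A concurrent comparator is not needed to correct the wording, and at pilot size it would not test efficacy: assuming 20% versus 40% conversion and two-sided alpha 0.05, power is about 22% with 15 dyads per arm and 39% with 30, and 80% power needs 82 per arm.
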